7.2.1. Discontinuation of Inadvertently Enrolled Participants

If the sponsor or investigator identify a participant who did not meet enrollment criteria and was inadvertently enrolled, then the participant should be discontinued from study treatment unless there are extenuating circumstances that make it medically necessary for the participant to continue on study treatment. If the investigator and the sponsor clinical research physician (CRP) agree it is medically appropriate to continue, the investigator must obtain documented approval from the sponsor CRP to allow the inadvertently enrolled participant to continue in the study with or without treatment with IP. Safety follow up is as outlined in Section 1.3 (Schedule of Activities), Section 8.3 (Adverse Events and Serious Adverse Events), and Section 8.2 (Safety Assessments) of the protocol.

7.3. Lost to Follow up

A study participant will be considered lost to follow-up if he or she repeatedly fails to return for scheduled visits and is unable to be contacted by the study site.

The following actions must be taken if a participant fails to return to the clinic for a required study visit:

- The site must attempt to contact the participant and reschedule the missed visit as soon as possible and counsel the participant on the importance of maintaining the assigned visit schedule and ascertain whether or not the participant wishes to and/or should continue in the study.
- Before a participant is deemed lost to follow-up, the investigator or designee must make every effort to regain contact with the participant (where possible, 3 telephone calls and, if necessary, a certified letter to the participant's last known mailing address or local

equivalent methods). These contact attempts should be documented in the participant's medical record.

- Should the participant continue to be unreachable, he/she will be considered to have withdrawn from the study.

Discontinuation of specific sites or of the study as a whole are handled as part of Section [10.1](#).

8. Study Assessments and Procedures

Study procedures and the study visits at which they are performed, including tolerance limits for the study visits, are listed in the Schedule of Activities (Section 1.3). Adherence to the study design requirements, including those specified in the Schedule of Activities, is essential and required for study conduct.

Efficacy and safety assessments included in this study are generally regarded as reliable and accurate with respect to the efficacy and safety assessments in individuals and populations with T1DM.

8.1. Efficacy Assessments

8.1.1. Primary Efficacy Assessment

The primary efficacy measure is HbA1c change from baseline to Week 26.

8.1.2. Secondary Efficacy Assessments

Secondary efficacy assessments for this study are:

- HbA1c change from baseline to Week 12
- FG change from baseline to Weeks 12 and 26
- Bolus insulin dose change from baseline to Weeks 12 and 26

8.2. Safety Assessments

Planned time points for all safety assessments are provided in the Schedule of Activities (Section 1.3).

The following safety assessments will be evaluated as secondary objectives:

- Incidence and rate of hypoglycemia
- Incidence of treatment-emergent SAEs
- Clinical laboratory assessments with specific focus on liver aminotransferase changes

8.2.1. Physical Examinations

A complete physical examination will include, at a minimum, assessments of the CV, Respiratory, Gastrointestinal and Neurological systems. Height and weight will also be measured and recorded.

Investigators should pay special attention to clinical signs related to previous serious illnesses.

Additionally, investigators should inspect injection sites during the physical examination.

8.2.2. Vital Signs

For each participant, vital signs measurements should be conducted according to the Schedule of Activities (Section 1.3).

Sitting blood pressure (BP) and pulse rate will be measured using automated electronic sphygmomanometer according to the Schedule of Activities (Section 1.3). Vital sign

measurements should be taken before obtaining an ECG tracing and before collection of blood samples for laboratory testing, at visits where required (see Schedule of Activities, Section 1.3). The participant should be required to sit quietly for 5 minutes before vital sign measurements are taken. An appropriately sized cuff (cuff bladder encircling at least 80% of the arm) should be used to ensure the accuracy of BP measurements. The arm used for the BP measurement should be supported at heart level. Blood pressure should be measured consistently using the same arm throughout the study. For each parameter (pulse rate, systolic BP, and diastolic BP), 3 measurements will be taken using the same arm; the recordings should be taken at least 1 minute apart, and each measurement of sitting pulse rate and BP will be recorded in the eCRF.

8.2.3. Electrocardiograms

For each patient, triplicate 12-lead digital ECGs and single safety ECGs will be collected according to the Schedule of Activities (Section 1.3). Patients must be supine for approximately 5 to 10 minutes before ECG collection and remain supine but awake during ECG collection. ECGs will be performed prior to collection of any blood samples.

ECGs will be interpreted by a qualified physician (the investigator or qualified designee) at the site as soon as possible after the time of ECG collection, and ideally while the patient is still present, to determine whether the patient meets entry criteria at the relevant visit(s) and for immediate patient management should any clinically relevant findings be identified.

Digital ECGs will be electronically transmitted to a central ECG laboratory designated by Lilly. The central ECG laboratory will perform a basic quality control check (e.g., demographics and study details) then store the ECGs in a database. At a future time, the stored ECG data may be overread at the central ECG laboratory for further evaluation of machine-read measurements or to meet regulatory requirements.

The machine-read ECG intervals and heart rate may be used for data analysis and report writing purposes unless an overread of the ECGs is conducted prior to completion of the final study report (in which case the overread data would be used).

8.2.4. Self-monitoring of Blood Glucose (SMBG)

At Visit 2, patients will receive the Dexcom G6 CGM device and training on its use, sensor placement, interpretation of CGM values and alarms, and the requirements for CGM. SMBG will be performed through this CGM device. In the receiver of the CGM device 2 alarm settings are mandatory: an hypoglycemia alarm at 70mg/dl and a hypoglycemia alarm at 55mg/dl. Glucose readings should be obtained for monitoring patient safety (hypoglycemia) and may be checked as frequently as necessary. Patients should record 6-point glucose profiles in the eDiary provided, prior to the visits indicated by the Schedule of Activities (Section 1.3). Patients with missing eDiary glucose entries should be retrained on the importance of glucose reporting in the eDiary.

Patients will be instructed to record a prebreakfast (fasting) reading every morning and to record all results in the eDiary. Patients will also review BG using the CGM device as needed to evaluate symptoms of hypoglycemia.

Patients will be instructed to record 6-point glucose profiles over a 24-hour period on 2 nonconsecutive days during the 7-day period prior to visits indicated in the Schedule of

Activities (Section 1.3) using their CGM sensor. The 6-point profile consists of pre-meal and 2-hour postprandial glucose readings for the morning, midday, and evening meals in 1 day. Pre-meal measurements should be taken before the patient begins eating the meal. Patients should record their glucose measurements in their eDiaries and bring the diary to the investigative site at each study visit.

Participants are permitted to use a personal glucose meter for additional monitoring if deemed necessary or by personal choice. This data, however, should not be used for dosing decisions within the study as long as the CGM system is functional. In case of technical issues or during the calibration period of the CGM system a personal BG meter can be used for therapeutic decision making.

8.2.5. Clinical Safety Laboratory Assessments

See Section 10.2 for the list of clinical laboratory tests to be performed and the Schedule of Activities (Section 1.3) for the timing and frequency.

The investigator must review the laboratory report, document this review, and record any clinically relevant changes occurring during the study in the AE section of the eCRF. The laboratory reports must be filed with the source documents. Clinically significant abnormal laboratory findings are those, which are not associated with the underlying disease, unless judged by the investigator to be more severe than expected for the participant's condition.

All laboratory tests with values considered clinically significantly abnormal during participation in the study or within 6 weeks after the last dose of study intervention (i.e., within the follow up period) should be repeated until the values return to normal or baseline or are no longer considered clinically significant by the investigator or Lilly medical.

- If such values do not return to normal/baseline within a period of time judged reasonable by the investigator, the etiology should be identified and the sponsor notified.
- All protocol-required laboratory assessments, as defined in Section 10.2, must be conducted in accordance with the laboratory manual and the Schedule of Activities.
- If laboratory values from non-protocol specified laboratory assessments performed at the institution's local laboratory require a change in participant management or are considered clinically significant by the investigator (e.g., SAE or AE or dose modification), then the results must be recorded in the eCRF.

8.2.6. Safety Monitoring

The principal investigator will monitor safety and laboratory data throughout the study and should discuss safety concerns with the sponsor immediately upon occurrence or awareness of the concern to determine whether the participant should continue or discontinue study drug.

8.2.6.1. Hepatic Safety Monitoring

If a study patient experiences elevated ALT ≥ 3 ULN, ALP ≥ 2 ULN, or elevated TBL ≥ 2 ULN, liver testing (Section 10.5) should be repeated within 3 to 5 days including ALT, AST, ALP, TBL, direct bilirubin, gamma-glutamyl transferase, and creatine kinase to confirm the abnormality and to determine if it is increasing or decreasing. If the abnormality persists or

worsens, clinical and laboratory monitoring should be initiated by the investigator and in consultation with the study Lilly Medical. Monitoring of ALT, AST, TBL, and ALP should continue until levels normalize or return to approximate baseline levels.

Hepatic Safety Data Collection

Additional safety data should be collected via the eCRF if 1 or more of the following conditions occur:

- elevation of ALT to ≥ 5 X ULN on 2 or more consecutive blood tests
- elevated TBL to ≥ 2 X ULN (except for cases of known Gilbert's syndrome)
- elevation of ALP to ≥ 2 X ULN on 2 or more consecutive blood tests
- patient discontinued from treatment due to a hepatic event or abnormality of liver tests
- hepatic event considered to be a SAE

8.2.7. Body Weight

Body weight will be measured at prespecified time points (see Schedule of Activities, Section 1.3). Patients will be weighed in a light hospital gown or standard clinical research site scrubs at approximately the same time in the morning after an overnight fast and after evacuation of bowel and bladder contents, if possible.

Weight will be measured once at screening (non-fasting) and recorded in the source document and eCRF. At lead-in and randomization (Visit 2 and Visit 3, respectively) and all subsequent visits indicated in the Schedule of Activities (Section 1.3), weight will be measured twice, with the patient stepping off the scale between measurements.

Both weight measurements will be recorded in the source document and the eCRF. Calibrated (within 6 months prior to study start) scales should be used. The same scale should be used for all weight measurements throughout the study and should not be moved during the conduct of the study.

8.3. Adverse Events and Serious Adverse Events

All AEs will be reported by the participant (or, when appropriate, by a caregiver, surrogate, or the participant's legally authorized representative).

The investigator and any qualified designees are responsible for detecting, documenting, and recording events that meet the definition of an AE or SAE and remain responsible for following up AEs that are serious, are considered related to the study intervention or study procedures, or that caused the participant to discontinue the study intervention or the study (see Section 7).

8.3.1. Time Period and Frequency for Collecting AE and SAE Information

All AEs occurring after signing the ICF are recorded in the eCRF and assessed for serious criteria.

The SAE reporting to sponsor begins after the patient has signed the ICF and has received study drug. However, if an SAE occurs after signing the ICF, but prior to receiving LY3209590, it needs to be reported ONLY if it is considered reasonably possibly related to study procedures.

All SAEs will be recorded and reported to the sponsor or designee immediately and under no circumstance should this exceed 24 hours, as indicated in Section 10.3. The investigator will submit any updated SAE data to the sponsor within 24 hours of it being available.

Investigators are not obligated to actively seek AE or SAE after conclusion of the study participation. However, if the investigator learns of any SAE, including a death, at any time after a participant has been discharged from the study, and he/she considers the event to be reasonably related to the study intervention or study participation, the investigator must promptly notify the sponsor.

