6.4. Study Intervention Compliance

The assessment of treatment compliance with IP (LY3209590 or insulin degludec) will be determined by the following:

- Information about the once weekly IP injections administered at home by the patient will be entered into the patient diary by the patient and reviewed by the site personnel at each study visit; this information will be collected in the electronic study diary;
- IP accountability will be checked according to the Schedule of Activities (Section 1.3). Study participants will be instructed to return all dispensed vials, any *unused* pens, and/or all empty cartons at the next visit to the study site for the purpose of performing drug accountability.

Other aspects of compliance will also be assessed at each visit, including the patient's adherence to the visit schedule, compliance with the concomitant short acting insulin requirements and other medication guidances (Section 6.5), completion of study diaries, results of SMBG through CGM, and any other parameters the investigator considers necessary. Patients considered to be poorly compliant with their medications and/or study procedures (e.g., missed visits or specific diagnostic tests) will receive additional training and instructions, as required.

When participants are dosed at the site, they will receive IP directly from the investigator or designee, under medical supervision. The date and time of each dose administered in the clinic will be recorded in the source documents and recorded in the diary.

When participants administer study treatment at home, compliance with study treatment will be assessed at each visit. Compliance will be assessed by direct questioning, reviewing eCOA documentation, counting returned pens, etc. during the site visits.

A record of the number of the pens and study medications dispensed to and taken by each participant must be maintained and reconciled with study intervention and compliance records. Intervention start and stop dates, including dates for intervention delays and/or dose reductions will also be recorded in the electronic case report form (eCRF).

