10.3.3. Recording and Follow-Up of AE and/or SAE**AE and SAE Recording**

- When an AE/SAE occurs, it is the responsibility of the investigator to review all documentation (e.g., hospital progress notes, laboratory reports, and diagnostics reports) related to the event.
- The investigator will then record all relevant AE/SAE information in the CRF.
- It is **not** acceptable for the investigator to send photocopies of the participant's medical records in lieu of completion of the AE/SAE CRF page.
- There may be instances when copies of medical records for certain cases are requested by sponsor. In this case, all participant identifiers, with the exception of the participant number, will be redacted on the copies of the medical records before submission to sponsor.
- The investigator will attempt to establish a diagnosis of the event based on signs, symptoms, and/or other clinical information. Whenever possible, the diagnosis (not the individual signs/symptoms) will be documented as the AE/SAE.

Assessment of Intensity

The investigator will make an assessment of intensity for each AE and SAE reported during the study and assign it to 1 of the following categories:

- Mild: An event that is easily tolerated by the participant, causing minimal discomfort and not interfering with everyday activities.
- Moderate: An event that causes sufficient discomfort and interferes with normal everyday activities.
- Severe: An event that prevents normal everyday activities. An AE that is assessed as severe should not be confused with a SAE. Severe is a category utilized for rating the intensity of an event; and both AEs and SAEs can be assessed as severe.

An event is defined as ‘serious’ when it meets at least 1 of the predefined outcomes as described in the definition of an SAE, NOT when it is rated as severe.

Assessment of Causality

- The investigator is obligated to assess the relationship between study intervention and each occurrence of each AE/SAE.
- A “reasonable possibility” of a relationship conveys that there are facts, evidence, and/or arguments to suggest a causal relationship, rather than a relationship cannot be ruled out.
- The investigator will use clinical judgment to determine the relationship.
- Alternative causes, such as underlying disease(s), concomitant therapy, and other risk factors, as well as the temporal relationship of the event to study intervention administration will be considered and investigated.

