4.2.2. Safety

To investigate the safety of LY3209590 compared with insulin degludec for the following endpoints:

1. Incidence and rate of hypoglycemia events during the treatment period
2. Incidence of treatment-emergent serious adverse events (TE-SAEs)

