5.10.1. Study Drug Exposure

Exposure in days in the study will be calculated for each patient and summarized by treatment group. Exposure during the treatment period will be calculated from date of first study basal insulin dose collected in the electronic case report form (eCRF) to date of discontinuation from study treatment (i.e., the last dose date for insulin degludec, and the last dose date + 7 days for LY3209590). The sum of exposure in total patient years will also be provided.

Frequency of subjects falling into the following different exposure ranges will also be summarized: >0 days, ≥ 7 days, ≥ 14 days, ≥ 30 days (1 month), ≥ 60 days (2 months), ≥ 90 days (3 months), ≥ 120 days (4 months), ≥ 183 days (6 months) days.

In addition, the duration of follow-up in days for each individual patient is calculated from the date of last dose of study drug for insulin degludec or the date of last dose of study drug + 7 days for LY3209590 to the last study visit date. The duration of the follow-up in days will be summarized (n, mean, standard deviation, minimum, maximum median, and sum in total patient years) by treatment group.

The duration on study from date of the first study drug to the last study visit date (including the follow-up visit) will also be summarized by treatment group, the following summary statistics will be provided: n, mean, standard deviation, median, minimum, maximum, and sum in total patient years.

A by-patient listing of drug exposure data will be created to provide data for the CSR.

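### Protocol 8.3.1 ends the pre-dose SAE reporting exception at receipt of LY3209590, a point that degludec participants never reach, and so contradicts its own study-drug rule

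*Protocol*

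**What the plan says.** Protocol Section 8.3.1 makes four statements on collecting and reporting events.

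1. Recording: "All AEs occurring after signing the ICF are recorded in the eCRF and assessed for serious criteria".
2. Start of sponsor reporting: "The SAE reporting to sponsor begins after the patient has signed the ICF and has received study drug".
3. Exception, introduced as a qualification of statement 2: an SAE may occur after consent, "but prior to receiving LY3209590, it needs to be reported ONLY if it is considered reasonably possibly related to study procedures".
4. Speed: "All SAEs will be recorded and reported to the sponsor or designee immediately and under no circumstance should this exceed 24 hours".

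Statements 1, 2 and 4 do not distinguish between arms. Statement 3 names one arm's product.

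Elsewhere both products are treated as study drug. Protocol Section 6.4 says: "The assessment of treatment compliance with IP (LY3209590 or insulin degludec) will be determined by the following". SAP Section 5.10.1 refers to "the date of last dose of study drug for insulin degludec".

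The incidence of treatment-emergent SAEs is a secondary safety endpoint compared between LY3209590 and degludec (Protocol Section 3, SAP Section 4.2.2).

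**The concern.** An exception for the time before treatment should close at the first dose in either arm. This one closes only on receipt of LY3209590. In the LY3209590 arm that is the first dose. In the degludec arm it never happens, so the text leaves the narrow, procedure-related-only rule in force through the 26-week treatment period and the 5-week follow-up.

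What is at stake first is safety oversight. Protocol Section 8.3.4 treats prompt notification by the investigator as essential to the sponsor's legal and ethical duties. No data monitoring committee is planned (Protocol Section 9.6), and SAP Section 6 has the study team monitoring patient safety. That oversight depends on sites telling the sponsor about SAEs. The trial is open-label (Protocol Section 6.3), so a site knows which participants the literal exception would cover.

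The endpoint comes second. If SAEs were lost from the degludec arm alone, the comparison would tilt against LY3209590.

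**Working it through.** The plan states no figure on this point, so the check is a reading of the text.

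**Step 1. Does study drug include degludec?** Yes, by Protocol Section 6.4 and SAP Section 5.10.1 as quoted. Statement 2 therefore starts sponsor reporting at the first dose in either arm.

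**Step 2. Apply statements 2 and 3 to each situation.**

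| Situation | Statement 2 | Statement 3, read literally | Agree? |
|---|---|---|---|
| After consent, before first dose, either arm | Reporting not yet begun | Only procedure-related SAEs | Yes |
| After first dose of LY3209590 | Reporting begun | Exception closed | Yes |
| After first dose of degludec | Reporting begun | Exception still open | No |

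The conflict is confined to one cell, but that cell is the whole on-treatment and follow-up experience of the comparator arm: 26 + 5 = 31 weeks for a participant who completes. Protocol Section 9.2 plans about 119 participants per arm out of 238, and 119/238 = 50%.

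**Step 3. Does statement 4 settle it?** Not alone. If every SAE were always reportable, the exception would do nothing even before the first dose. Statement 4 has to be read subject to the exception, and the only end point the exception gives is receipt of LY3209590.

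**Step 4. What does the exception restrict?** Reporting to the sponsor. It does not restrict recording. Statement 1 covers all AEs after consent in both arms, and Protocol Section 10.3.3 adds, again without limit by arm: "The investigator will then record all relevant AE/SAE information in the CRF". The schedule of activities has AE/SAE review from Visit 3 onward for everyone.

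**Step 5. What feeds the endpoint?** SAP Section 5.10.2 counts treatment-emergent events from the first dose of study basal insulin, uses data to the end of the study, and summarizes treatment-emergent SAEs on the Safety Population. None of this is anchored on LY3209590. The SAP does not name the source dataset for the SAE summary. That it draws on the eCRF AE records is a reasonable inference, not a stated fact.

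**Step 6. Are any SAEs protected separately?** Confirmed severe hypoglycemia must be recorded as serious and reported to the sponsor as an SAE under Protocol Section 8.3.7.1. Allergic and injection-site reactions that meet a serious criterion have their own duty in Section 8.3.7.2. Neither depends on arm.

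**Step 7. Can the loss be sized?** No. The documents give neither an SAE rate nor any indication of how many sites would follow the literal wording. An event not notified to the sponsor is also not necessarily missing from the database.

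**The case against.** The strongest reply is that this is a slip of one word which context cures. The exception qualifies a sentence about when reporting begins, so its natural meaning is the time before the first dose. The literal meaning would defeat the sentence before it and the one after it for half the trial, and a sensible site would not read it that way. The primary endpoint, sample size and SAP methods are untouched.

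Much of this stands. The intended meaning is hardly in doubt, and most sites would probably follow it. But the exception is the more specific rule, it carries an emphatic restriction in capitals, and its stated end point is wrong for one arm. A safety-reporting rule should not need to be rescued by context in one arm only.

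A reader might go further and infer that the treatment-emergent SAE comparison is biased, or that severe hypoglycemia on degludec would go uncounted. The documents do not support either. Recording and seriousness assessment apply to both arms, the SAP's counting rule is neutral between arms, and severe hypoglycemia has its own reporting duty.

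**Conclusion.** Section 8.3.1 contradicts itself for degludec participants and should be corrected. The defect is one phrase in an operative safety rule. Its literal reach is the comparator arm, about half of those randomized, from first dose to the end of follow-up.

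The consequence that follows from the text is a risk of delayed or omitted SAE notification to the sponsor in that arm, and only if a site applies the literal wording. Nothing in the documents shows that any site has done so. Bias in the secondary SAE endpoint remains possible but not shown. It would require serious events to be missing from the analysis data as well as from sponsor reports. The judgment that this is unlikely rests on the inference that the SAE summary draws on the eCRF records. No count of missed events is offered, because any such count would rest on assumed rates alone.

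**What to change.** In the exception sentence of Protocol Section 8.3.1, replace receipt of LY3209590 as the end point with receipt of the first dose of study drug (LY3209590 or insulin degludec). A clarification letter to sites would do, with the text itself corrected at the next amendment. The wording cost is trivial. An amendment made for this alone would need ethics approval (Protocol Section 10.1.1), which is why the letter is the lighter route.

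Before database lock, reconcile SAE reports held by the sponsor against AEs marked serious in the eCRF, in both arms, and resolve any mismatch. This costs some data-management time. It finds events that were recorded but not notified; it cannot find events that were never recorded. If participant follow-up has already ended, the reconciliation is the part that still matters. It would also be worth stating in the SAP which dataset supplies the treatment-emergent SAE summary.
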